Data will be collected at several points. All potential participants will complete a 20-30-minute screener to determine eligibility. Eligible participants will then complete a baseline assessment, as well as follow-up assessments at 3, 6 and 12 months post-baseline. In addition, all participants will complete a biweekly symptom assessment, using the PHQ-9 and GAD-7, and the Paykel Suicide Screener, if necessary.

VII. Biostatistical Analysis

A. Specific data variables being collected for the study (e.g. data collection sheets).

Screener, Baseline Assessment, Follow-up Assessment, Symptom Assessment (PHQ-9 and GAD-7)

The proposed study has four goals:

- 1) To test the effectiveness of an evidence-based, CHW-led mental health intervention, The Strong Minds-Strong Communities Randomized Clinical Trial (RCT), focused on (1)

decreasing depression and anxiety symptoms, (2) improving functioning, and (3) increasing perceived quality of care among low-income racial, ethnic, and linguistic minorities.

- 2) To test whether there is a differential effect of Strong Minds-Strong Communities based on participants' race and ethnicity, thereby identifying whether the intervention can be particularly effective for certain racial and ethnic groups.
- 3) To test whether there is a differential effect of Strong Minds-Strong Communities based on participants' language, thereby identifying whether the intervention can be particularly effective for certain linguistic groups.
- 4) To test whether there is a differential effect of Strong Minds-Strong Communities in North Carolina compared to Massachusetts, thereby identifying whether the effectiveness of the intervention is associated with a specific geographic location.

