Moderators. In Goal 2, race and ethnicity will be used as a moderator of the main independent variable (intervention condition). Using self-reported information, participants will be classified into four mutually exclusive categories: Latinx, non-Latinx Black, Asian, and non-Latinx White. In Goal 3, language will be used as a moderator of the main independent variable (intervention condition). Using self-reported information, participants will be classified into four mutually exclusive categories: English, Spanish, Mandarin, and Cantonese. In Goal 4, the site of recruitment will be used as a moderator of the intervention condition. Participants will be classified into two mutually exclusive categories of place of residence: North Carolina or Massachusetts.

Endpoints. The primary endpoints will be change from baseline in depression and anxiety symptoms, level of functioning, and perceived quality of care at month 6 (end of intervention) and at month 12 (6-months post-intervention). The key secondary effectiveness endpoints will

be the change from baseline in the score on the CAT-MH depression (range 0 to 100 with higher scores indicating worse depression symptoms) and the CAT-MH anxiety (range 0 to 100 with higher scores indicating worse anxiety symptoms) at month 6 and 12. The primary and key secondary effectiveness endpoints will be also evaluated in prespecified subgroup analyses based on participant's race and ethnicity, language, and site. Other exploratory endpoints will include changes from baseline in HSCL-25, WHODAS 2·0, PoC-OP, CAT-MH depression, and CAT-MH anxiety scores at month 3, about midway through the intervention. Finally, the primary and key secondary effectiveness endpoints will be evaluated in exploratory subgroup analyses based on the participant's baseline severity of depression and anxiety.

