Statistical Analyses. A two-sided P value of 0·05 will be used to calibrate the significance and false discovery rate. For the primary and key secondary endpoints, we will employ a Benjamini-Hochberg step-down procedure to adjust for the multiple comparisons across 5 outcome scores (HSCL-25, WHODAS 2·0, PoC-OP, CAT-MH depression, and CAT-MH anxiety) at 2 follow-up points (months 6 and 12). If the lowest of the ten P values was less than 0·005 (0·05 ÷ 10), it will be considered to be significant; the second lowest P value will be considered to be significant if less than 0·0056 (0·05 ÷ 9); the third lowest P value will be significant if less than 0·006 (0·05 ÷ 8); and so on. Primary and key secondary efficacy endpoints will be separately analyzed using a general linear model to estimate the treatment effect. Except for PoC-OP, baseline outcome scores will be included as covariates in all analyses. Site (Massachusetts versus North Carolina) will also be included as covariate in all analyses. This general linear model has the following form:

$$y_{i,post-baseline} = \alpha_0 + \alpha_1 Intervention_i + \alpha_2 y_{i,baseline} + \alpha_3 site_i + \varepsilon_i$$

where $y_{i,post-baseline}$ represents an outcome measure for participant i at either 6- or 12-months post-baseline. $Intervention_i$ will be an effect-coded variable equal to -0.5 if participant i was randomized to the control group and equal to 0.5 if participant i was randomized to the intervention group. $y_{i,baseline}$ is the baseline measure of the outcome (except for PoC-OP), $site_i$ is a binary indicator equal to one if participant i was recruited in Massachusetts and equal to 0 if recruited in North Carolina, and ε_i is an error term. Because participants will be recruited in multiple CBOs/clinics across the two sites, in sensitivity analyses we will use generalized linear mixed models with a random intercept accounting for clustering within CBOs/clinics for each primary and key secondary effectiveness endpoint.

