We will conduct analysis of missing data at either endpoint (primary or exploratory) to test whether that, conditional on the observed baseline variables (including baseline outcome scores), the missing at random assumption is plausible. Missing data for all statistical models (primary and key secondary endpoints, exploratory endpoint, prespecified subgroup analyses and exploratory subgroups analyses) will be handled using model-based imputation. For example, missing values to analyze change from baseline in HSCL-25 scores at the 6-month endpoint will be imputed using a general linear model where HSCL-25 scores at month 6 will be the dependent variable. An effect coded variable for intervention condition, HSCL-25 scores at baseline, and a binary indicator for site (Massachusetts versus North Carolina) will be included as predictors. The model further will also include the auxiliary baseline variables associated with missingness (e.g., participant's age or gender). The same model-based imputation will be employed for all primary and key secondary endpoints, and the exploratory endpoint. Imputation models for subgroup analyses (prespecified and exploratory) will add the moderator and its interaction with intervention condition as predictors. For each model, 20 imputed datasets will be generated. Analyses of imputed data will use Rubin's rules to obtain pooled estimates and their standard errors.

C. Power Analysis (e.g., sample size, evaluable subjects, etc.)

The proposed study aimed to recruit 1,200 participants equally distributed across sites (North Carolina and Massachusetts) and intervention conditions (Intervention and Control). That is $N = 600$ intervention participants (300 in North Carolina and 300 in Massachusetts) and $N = 600$ enhanced usual care participants (300 in North Carolina and 300 in Massachusetts).

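### Missing outcomes are imputed from arm, site and baseline data only, although the same scores are scheduled at three follow-up visits, and no analysis covers departures from missing at random

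*Combined protocol and SAP*

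**What the plan says.** Section VII.B handles missing outcomes in every model by multiple imputation (20 datasets, Rubin's rules). Its example is the month-6 HSCL-25 score. Alongside the arm indicator, "HSCL-25 scores at baseline, and a binary indicator for site (Massachusetts versus North Carolina) will be included as predictors", and baseline auxiliaries related to missingness, such as age or gender, are added. The example is then generalised: "The same model-based imputation will be employed for all primary and key secondary endpoints, and the exploratory endpoint". Subgroup models add only the moderator and its product with arm, and every moderator (race and ethnicity, language, site, baseline severity) is a baseline characteristic.

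The same section will examine whether, "conditional on the observed baseline variables (including baseline outcome scores), the missing at random assumption is plausible".

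Section VII.A (Statistical Analyses) fits a separate linear model to each endpoint, with arm, baseline score and site as terms and one exception: "Except for PoC-OP, baseline outcome scores will be included as covariates in all analyses". It names one sensitivity analysis for the primary and key secondary endpoints: "in sensitivity analyses we will use generalized linear mixed models with a random intercept accounting for clustering within CBOs/clinics".

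On the data available, section VI.A schedules "follow-up assessments at 3, 6 and 12 months post-baseline". Section VII.A (Endpoints) lists all five scores at the first of these visits, ending with "CAT-MH depression, and CAT-MH anxiety scores at month 3, about midway through the intervention".

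**The concern.** Two things are missing.

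- **Information from other visits.** A participant seen at month 3 but not at month 6 has a recent score on the same scale, and the imputation ignores it. The same holds for months 3 and 6 when month 12 is missing. Apart from the auxiliaries, the imputation predictors are those of the analysis model, so the imputed values carry almost nothing that the complete cases do not already carry.
- **Any view of the result under another assumption.** The planned check of missing at random conditions on baseline variables only. Observed data cannot confirm that assumption in any case, and the one named sensitivity analysis concerns clustering.

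At stake are some precision, some protection against bias if dropout follows early symptom course differently in the two arms, and the reader's ability to judge how far a result rests on missing at random.

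There is also a wording query on PoC-OP. The analysis model omits its baseline score, while the imputation template includes a baseline score and is said to apply to all endpoints. The plan does not say which holds when PoC-OP is imputed.

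**Working it through.** **Inputs from the plan (section VII.C).** 1,200 enrolled; 13% nonparticipation; 1200 x (1 - 0.13) = 1044, which reproduces the stated effective sample; effect size used for power 0.20; expected effects 0.24 to 0.68. (The stated 87% power comes out at 89.8% with 522 per arm; that is a separate matter and nothing below uses it.)

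**Assumptions, not in the documents.** The 13% is treated as missingness at the endpoint. Correlation of baseline with each follow-up score: rb = 0.4 to 0.6. Correlation between follow-up scores: r = 0.6 to 0.75. Share of dropouts who have the earlier score: s = 0, 0.5 or 1.

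**1. Why imputation adds little.** If the imputation and analysis models have the same predictors, the imputed values lie around the line fitted to the complete cases, and refitting returns that line. In simulation with single regression imputation and no auxiliaries, the two estimates agreed to 1e-15. With 20 random imputations and auxiliaries the match is approximate.

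**2. Precision.** Variance reduction = partial R² x (1 - 0.87/(0.87 + 0.13s)). The second factor is 0, 0.0695 and 0.13 for s = 0, 0.5 and 1.

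- Month 6 from month 3: partial r = (r - rb²)/(1 - rb²), from (0.6 - 0.36)/0.64 = 0.375 to (0.75 - 0.16)/0.84 = 0.702.
- Month 12 from months 3 and 6: partial R² = 0.205 to 0.580.
- PoC-OP at month 6, if no baseline term is used: partial R² = r² = 0.36 to 0.5625.

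| Variance reduction | s = 0 | s = 0.5 | s = 1 |
|---|---|---|---|
| Month 6 | 0% | 1.0-3.4% | 1.8-6.4% |
| Month 12 | 0% | 1.4-4.0% | 2.7-7.5% |
| PoC-OP, no baseline term | 0% | 2.5-3.9% | 4.7-7.3% |

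A simulation of 4000 trials (rb 0.6, r 0.75) gave a 4.9% gain at month 6, against 4.8% by the formula.

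**3. Bias if dropout depends on the month-3 score.** Simulated with 1.5 million records per setting, a true month-6 effect of -0.20 SD and a month-3 effect of -0.10 or -0.20 SD. Graded dropout is logistic in the month-3 score, slope 0.5 or 1.0 per SD, 13% missing.

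- Same graded rule in both arms: bias of baseline-only imputation at most 0.011 SD.
- Same sharp cut-off in both arms, removing 2-13%: 0.002-0.038 SD.
- Graded in controls only, with 13% unrelated to severity in the intervention arm: 0.015-0.069 SD, towards no effect.

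Adding month 3 to by-arm imputation in the controls-only case leaves about 0.001 SD if all dropouts have a month-3 score. At slope 1.0, a bias of about 0.028-0.070 SD falls to 0.013-0.032 SD if half have one. It does not fall if none do.

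**4. Departures from missing at random.** With 13% missing in one arm, moving its imputed values by delta moves the effect by 0.13 x delta: 0.013, 0.039 or 0.065 SD for delta = 0.1, 0.3 or 0.5 SD. SE = 2/√1044 x √(1 - rb²) = 0.0567 (rb 0.4) to 0.0495 (rb 0.6), held fixed. Significance is lost at delta = (estimate - z x SE)/0.13.

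- Estimate 0.20, z = 1.960: (0.20 - 0.1112)/0.13 = 0.68 to (0.20 - 0.0971)/0.13 = 0.79 SD.
- Estimate 0.24, z = 1.960: (0.24 - 0.1112)/0.13 = 0.99 to (0.24 - 0.0971)/0.13 = 1.10 SD.
- At P<0.005 (z = 2.807), which section VII.A applies only to the smallest of ten P values: 0.31-0.47 SD for 0.20, and 0.62-0.78 SD for 0.24.

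**The case against.** Multiple imputation from baseline is a legitimate analysis under its stated assumption, and the auxiliaries are chosen because they relate to missingness, which is exactly where the plan differs from a complete-case analysis. The gains from using other visits are modest. The larger biases need dropout that follows month-3 severity in one arm only. The 13% is described as nonparticipation of enrolled people; if these people never engage after enrolment, they have no month-3 score either, and the change gains nothing at month 6. The plan expects effects of 0.24 or more, so tipping points at 0.20 show it at its most fragile.

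All of this stands as a limit on size. It does not supply the missing sensitivity analysis, and it gives no reason to set aside scores that are already scheduled.

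A reader might go further and infer that severe controls leave the trial and that their lost outcomes bias the comparison, because section VI lets controls be removed from their group on severity. The documents do not support that. The same section has all enrolled participants contacted through month 12, with telephone, letter and home-visit steps. Section VIII.A allows some referred participants to continue. Section VII.A codes arm by allocation: -0.5 for a participant who "was randomized to the control group and equal to 0.5 if participant i was randomized to the intervention group". Only if removed controls lacked later scores could the effect be attenuated by this route, and no removal rate is given, so no figure can be put on it.

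**Conclusion.** The point holds as an improvement the plan should make, not as a flaw that invalidates the analysis. On the text it is firm: no follow-up score enters any described imputation model, and no analysis departs from missing at random. Its size is modest and conditional. The precision and bias figures rest on assumed correlations, on reading 13% as endpoint missingness, and on how many dropouts were seen earlier. The tipping points rest on the baseline correlation, on 13% missing in the shifted arm, and on a fixed standard error. At the low end of the plan's expected effects, only a large one-arm departure, around 1 SD, would overturn P<0.05; a reader should be able to see that from the trial's own data.

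It would be too strong to conclude that PoC-OP values will be imputed without any PoC-OP measurement. Its exception is written for the analysis covariates, and section VII.B can be read either way.

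**What to change.** 1. Impute months 3, 6 and 12 together (joint or chained model), separately by arm. Keep site, the auxiliaries, the planned moderator terms, and the baseline score where one is used. State what the PoC-OP imputation model contains. This corrects only dropout that observed scores explain.
2. Add a delta-adjusted (tipping-point) sensitivity analysis for the primary endpoints, with the shift varied by arm.
3. Reconcile sections VI and VIII.A on removal with the 12-month contact of all enrolled participants in section VI.

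The cost is SAP wording, modest programming and one more sensitivity analysis. No new data are needed.

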The target sample size was designed to achieve adequate power for our research questions. Using data from prior studies on the effectiveness of similar interventions, the estimated effect size for the outcomes ranged from 0·24 to 0·68. The nonparticipation rate of enrolled participants was assumed to be 13%. Our sample size of 1,200 (600 treatment and 600 control) from North Carolina and Massachusetts is thus effectively 1044. This sample yielded 87% power to detect an intervention effect size of 0·20, with a two-sided significance level of 0·05. Testing whether there is a differential effect of Strong Minds-Strong Communities based on participants' race and ethnicity means trying to determine whether race and ethnicity moderated the impact of the intervention. The racial and ethnic composition of our sample was roughly 63% Latinx, 14% non-Latinx Black, 13% Asian, 9% White, and 1% other races or ethnicities. Assuming a large effect size of the intervention for White participants ($> 0\cdot5$), a small effect size for Black participants ($< 0\cdot3$), and a medium effect size for Asian and Latinx participants ($> 0\cdot3$ and $< 0\cdot5$), we will have 80% power to detect a significant intervention effect in each racial and ethnic group with a sample size of 1044. Similarly, testing whether there is a differential effect of Strong Minds-Strong Communities in North Carolina compared to Massachusetts means testing whether site moderated the impact of the intervention.

VIII. Risks and Discomforts

A. Psychosocial (non-medical) risks:

The safety of intervention participants will be closely monitored during the Strong Minds-Strong Communities intervention. Participants will be administered the PHQ-9 depression screener and the GAD-7 anxiety screener during research interviews and biweekly during intervention sessions, and in biweekly check-ins for usual care participants. If participants endorse the Item

9 suicidality question of the PHQ-9, they will be administered the Paykel Suicidality Screener.

Those who endorse questions 4 and 5 of the Paykel, suggesting active suicidality, will be provided emergency care following emergency protocol developed by the research team.

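### Twenty imputations with no fixed seed leave borderline primary and key secondary verdicts dependent on the random draw; a larger m reduces this at little cost

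*Combined protocol and SAP*

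**What the plan says.** Section VII.B (Missing data) applies model-based multiple imputation to all statistical models. Each endpoint has its own imputation model, with arm, baseline score, site and auxiliary baseline variables as predictors. On the number of imputations it says only: "For each model, 20 imputed datasets will be generated". On pooling: "Analyses of imputed data will use Rubin's rules to obtain pooled estimates and their standard errors". No seed is fixed, the choice of 20 is not justified, and no Monte Carlo error is to be reported.

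The Statistical Analyses paragraph of section VII.A sets an ordered decision rule for ten P values (five scores at months 6 and 12). It opens with "If the lowest of the ten P values was less than 0·005 (0·05 ÷ 10), it will be considered to be significant". From there the divisor falls by one at each step: 0.05/9, printed as 0.0056, for the next smallest, then 0.05/8, printed as 0.006, and onward in the same way. The overall level is given as "A two-sided P value of 0·05 will be used to calibrate the significance and false discovery rate".

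The only figure bearing on the amount of missing data is in section VII.C (Power Analysis): "The nonparticipation rate of enrolled participants was assumed to be 13" per cent. On that basis the section reduces the 1,200 enrolled to an effective 1,044. No missing rate per endpoint and no fraction of missing information is given.

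**The concern.** A P value pooled over a finite number of imputations is partly a random quantity: repeat the imputation with another seed and it moves, although the data have not changed. Every primary and key secondary verdict here is a comparison of such a P value with a fixed threshold. If the movement is not small relative to the distance between the P value and its threshold, the verdict depends on the run. Because the rule is sequential, a change at an early step can also change the verdict on the endpoints after it. With no seed in the plan, which run is reported is left to the analyst. What is at stake is the reproducibility of borderline primary verdicts, not the validity of the test.

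**Working it through.** **Inputs.** From the plan: m = 20, Rubin's rules, thresholds 0.05/10, 0.05/9, 0.05/8 and so on, N = 1,200 with effective N of 1,044. Assumed: fraction of missing information (FMI) of 13%, taken from the nonparticipation rate. The proxy is reasonable because the imputation models use baseline predictors only, but it is still an assumption, so a range is shown.

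**The plan's own figures.** 0.05/10 = 0.005; 0.05/9 = 0.0056; 0.05/8 = 0.00625, printed as 0.006. 1,200 × 0.87 = 1,044. These reproduce.

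**Step 1: hand approximation of the noise in a P value near 0.005.** Put the total variance of the estimate at 1, so that the between-imputation variance is B = 0.13. P = 0.005 corresponds to z = 2.81.

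- Noise in the pooled estimate: √(B/m) = √(0.13/20) = 0.081.
- Noise from estimating B: relative SD √(2/19) = 0.32; effect on z about ½ × 0.13 × 0.32 × 2.81 = 0.06.
- Combined: √(0.081² + 0.06²) ≈ 0.10.
- Slope of the two-sided P value at z = 2.81: about 0.0155. SD of P ≈ 0.10 × 0.0155 ≈ 0.0016, before curvature and degrees-of-freedom effects.

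**Step 2: simulation of Rubin's rules** (pooled estimate ~ N(Q, B/m), estimated B ~ B·χ²(m−1)/(m−1), Barnard-Rubin degrees of freedom). At 13% FMI and m = 20 the SD is 0.00175, with 5th to 95th percentiles of about 0.0031 to 0.0088. Repeating full regression imputation on one simulated data set (N = 1,200, about 14% missing) gave an SD of 0.0018. There, 95% of runs fell between 0.0025 and 0.0095, and 52% fell below 0.005.

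SD of a P value near 0.005:

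| FMI | m = 20 | m = 200 |
|---|---|---|
| 5% | 0.0009 | 0.0003 |
| 10% | 0.0014 | 0.0004 |
| 13% | 0.0018 | 0.0005 |
| 20% | 0.0025 | 0.0007 |
| 30% | 0.0038 | 0.0009 |

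At 25% FMI and m = 20 it is 0.0032. At 13%, m = 50 gives 0.0010 and m = 100 gives 0.0007.

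**Step 3: how often two runs disagree.** Pairs of independent imputation runs on the same data were put through the plan's printed thresholds for ten endpoints (common effect d, assumed correlation 0.5, FMI 13%). Disagreement means that the two sets of significant endpoints differ in at least one endpoint.

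| d | m = 20 | m = 200 |
|---|---|---|
| 0.10 | 19% | not quoted |
| 0.15 | 28% | about 10% |
| 0.20 | 20% | 7% |
| 0.24 | 9% | 3% |
| 0.30 | under 1% | not quoted |
| 0.40 | about 0% | not quoted |

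Section VII.C bases its power statement on d = 0.20 and gives 0.24 to 0.68 as the range of effects expected from earlier studies.

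**The case against.** The strongest objection is that m = 20 is not an error. Rubin's rules already carry the finite-m noise in the (1 + 1/m)B term. A simulated test under the null at the 0.005 level with m = 20 rejected at 0.00499, and the inflation of the variance is only 0.13/20 = 0.65%. Nor is the risk large across the plan's expected effects: 9% at 0.24, the bottom of that range, and negligible from 0.30 up. Both statements stand. They make this a matter of precision and reproducibility.

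A reader might also compare the noise with the spacing of the thresholds. The first gap is 0.05/9 − 0.05/10 = 0.00056, and 0.00175/0.00056 is about 3.1, so it is tempting to conclude that the noise in every P value swamps the decision rule. The documents do not support that, for three reasons.

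- The ratio is below 1 from the 0.0125 threshold upward, and a P value of 0.0001 has an SD of only 0.00007.
- At the first threshold the ratio runs from 0.9 to 6.9 as FMI goes from 2% to 30%, and the plan gives no FMI.
- The gap is the wrong yardstick. A verdict changes when a P value lies close to its own threshold, wherever the next one is. The section names Benjamini-Hochberg but prints Holm-type cut-offs. Under the standard Benjamini-Hochberg cut-offs (0.005, 0.010, 0.015 and so on) the first gap is nine times wider, yet disagreement at d = 0.20 is about 16% against 20%.

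The point therefore does not depend on how that naming conflict is settled.

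**Conclusion.** The point holds as a low-cost improvement. At m = 20 and about 13% missing information, a P value near the strictest threshold has a Monte Carlo SD of about 0.0018 (0.0009 at 5% and 0.0032 at 25%). The set of endpoints declared significant then differs between two runs about 20% of the time at d = 0.20 and 9% at d = 0.24. These percentages rest on three assumptions that the plan does not supply: FMI of 13%, a correlation of 0.5 between endpoints, and the same effect on all ten.

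Two stronger conclusions might be inferred and should not be. Type I error is not inflated, because Rubin's rules account for finite m. And raising m does not make the result independent of the seed: at m = 200 two runs still disagree about 7% of the time at d = 0.20.

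**What to change.** In section VII.B:

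- Raise the number of imputations from 20 to at least 200 for the primary and key secondary models.
- Fix the random seed in the SAP. This makes the reported run repeatable and removes any choice between runs; it does not itself reduce the noise.
- Report the Monte Carlo error of each pooled P value, and pre-specify that m is raised further when a P value lies within two Monte Carlo standard errors of its own threshold.

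The cost is computing time: minutes for the linear models, slightly longer for the mixed-model sensitivity analyses planned in section VII.A. Sample size, data collection and the decision rule are unchanged.

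### The stated 87% power does not follow from the plan's own inputs, which give about 90%; the error is small and conservative, and one sentence corrects it

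*Combined protocol and SAP*

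**What the plan says.** Section VII.C (Power Analysis) gives every input to its own calculation.

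- Attrition: "The nonparticipation rate of enrolled participants was assumed to be 13" per cent.
- Sample after attrition: "Our sample size of 1,200 (600 treatment and 600 control) from North Carolina and Massachusetts is thus effectively 1044".
- Result: "This sample yielded 87% power to detect an intervention effect size of" 0.20, "with a two-sided significance level of 0·05".

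The same section puts the effects expected from prior studies at 0.24 to 0.68, so 0.20 lies just below that range. It mentions no intraclass correlation, design effect, baseline correlation, unequal allocation, adjusted significance level or second layer of attrition.

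The Statistical Analyses paragraph of section VII.A sets the primary model: a general linear model with site and, except for PoC-OP, the baseline score as covariates. Clustering within CBOs and clinics enters only in sensitivity analyses. The same paragraph applies a step-down rule to ten P values (five scores at two time points), with 0.005 as the threshold for the smallest.

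**The concern.** A stated power should be reproducible from the inputs printed beside it. Here the sample in the power sentence is the 1,044 just derived, and the effect size, significance level and sidedness are all given, so the result is fixed apart from small differences in method. It comes out at about 90%, not 87%.

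The gap is small, but its possible causes call for different corrections. A slip needs one number changed. A clustering allowance should be declared, because the primary model ignores clustering. A smaller analysis set would conflict with the 1,044 in the same paragraph and with section VII.B, which imputes missing outcomes. As written, a reader cannot tell which of these applies.

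**Working it through.** **Inputs** (all from VII.C unless marked)

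- Enrolled: 1,200, allocated 600 and 600
- Nonparticipation: 13%
- Effect size: d = 0.20 (standardised, so SD = 1)
- Significance level: two-sided 0.05
- Assumption, not in the plan: equal loss in the two arms

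**Step 1. Effective sample.** 1,200 × (1 − 0.13) = 1,044, or 522 per arm. This reproduces the plan's figure exactly.

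**Step 2. Power at the stated inputs.** By the normal approximation, power = Φ(d√(n/2) − z₀.₉₇₅).

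- d√(n/2) = 0.20 × √261 = 0.20 × 16.155 = 3.231
- 3.231 − 1.960 = 1.271
- Φ(1.271) = 0.898

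The exact noncentral t calculation on 1,042 degrees of freedom also gives 0.898. The difference from the stated figure is 89.8 − 87 = 2.8 points.

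**Step 3. Does any ordinary variant of the stated inputs give 87%?** (Noncentral t throughout.)

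| Variant | Power |
|---|---|
| No attrition, N = 1,200 | 93.3% |
| Attrition taken as 1,200/1.13, N about 1,062 | 90.2% |
| Most unequal split of 1,044 possible with 600 per arm (600/444) | 89.1% |
| Effect size at the lower rounding limit of 0.20, d = 0.195 | 88.2% |
| Baseline adjustment, assumed correlation 0.3 to 0.5 | 92.3% to 96.1% |

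None does. Baseline adjustment, which VII.A plans for every outcome except PoC-OP, moves further from 87%.

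**Step 4. What would give 87%?** With z₀.₈₇ = 1.126, the required sum is 1.960 + 1.126 = 3.086.

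- *Sample:* n per arm = 2 × (3.086/0.20)² ≈ 476, about 953 in total; about 954 by noncentral t. Totals from 941 to 969 round to 87%. A total of 954 would mean attrition of 1 − 954/1,200 = 20.5%, against the stated 13%.
- *Design effect:* 1,044/954 = 1.09. For illustration, with assumed values, clusters of 10 and an intraclass correlation of 0.01 give 1 + 9 × 0.01 = 1.09 and 87.2% power (normal approximation).
- *Effect size:* 3.086/16.155 = 0.191.
- *Significance level:* about 0.036.

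None of these stands in the plan.

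**Step 5. The first-step threshold, for context.** At two-sided 0.005, z = 2.807 and 3.231 − 2.807 = 0.424. Φ(0.424) = 0.664, or 66.2% by noncentral t. This is the unadjusted chance that one endpoint, named in advance, has P below 0.005 when d = 0.20.

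**The case against.** The strongest reply is that nothing depends on the difference. The stated figure is lower than the recomputed one, so the trial has more power than claimed. The target of 1,200, the 1,044, the model and the decision rules all stay as they are. The plan also expects effects of at least 0.24, where power at 0.05 is 97%. All of this stands, and it makes the point minor. It does not make 87% the right answer to the calculation the section describes.

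A reader might go further and infer that the design really delivers only about 66%, because the multiplicity rule begins "If the lowest of the ten P values was less than" 0.005. The documents do not support that.

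- The power sentence says openly that it is at two-sided 0.05, so quoting it there is not an arithmetic error.
- The 0.005 threshold applies only to the smallest of ten P values, and later thresholds relax. Suppose that all ten tests have d = 0.20 and a common correlation of 0.3 to 0.7 (assumed, simulated). The smallest P value then passes 0.005 with probability 92% to 99%, and average power per endpoint under the full step-down is about 77% to 79%.
- The 66% ignores baseline adjustment. With an assumed baseline correlation of 0.3 to 0.6, single-test power at 0.005 is 72% to 89%. At d = 0.24 it is 86% even without adjustment.

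Power under the ten-test procedure is a fair question, but a separate one.

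**Conclusion.** On the plan's own inputs, power is 89.8%, not 87%. The result assumes equal loss in the two arms and an unadjusted two-sample comparison. The most unequal loss possible lowers it only to 89.1%, and baseline adjustment raises it. The error is conservative by 2.8 points, and on these inputs the sample size need not change.

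The cause cannot be established from the documents. A reader might infer a concealed analysis population or an undeclared design effect, but those are not the only possibilities. A slip is just as consistent with the text: 87% is also the retention rate, 100% − 13%, though nothing confirms that link. Nor does matching the figure to a particular excluded subgroup carry weight. Any total from 941 to 969 rounds to 87%, and no section describes a main analysis that leaves out an eligible group.

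**What to change.** Change one sentence in VII.C, in one of two ways.

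1. If 87% is a slip, say that 1,044 participants (522 per arm) give about 90% power for a single test at two-sided 0.05 and an effect size of 0.20.
2. If 87% came from a smaller analysis set or a clustering allowance, state that N or design effect in VII.C and make it consistent with the analysis in VII.A, where clustering is now only a sensitivity analysis.

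If power at 0.005 is also reported, label the 66% as unadjusted power for one pre-named endpoint at the strictest step, not as the power of the ten-test procedure.

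The cost is a line of text. No new data, sample size or decision rule is involved.
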